# 8.3.4 Clinical Safety Laboratory Assessments

Refer to Appendix 2 for the list of clinical laboratory tests to be performed and to the SoA for the timing and frequency.

- The investigator or medically qualified designee (consistent with local requirements) must review the laboratory report, document this review, and record any clinically relevant changes occurring during the study in the AE section of the CRF. The laboratory reports must be filed with the source documents. Clinically significant abnormal laboratory findings are those which are not associated with the underlying disease, unless judged by the investigator to be more severe than expected for the participant's condition.
- All protocol-required laboratory assessments, as defined in Appendix 2, must be conducted in accordance with the laboratory manual and the SoA.
- If laboratory values from nonprotocol-specified laboratory assessments performed at the institution's local laboratory require a change in study participant management or are

considered clinically significant by the investigator (eg, SAE or AE or dose modification), then the results must be recorded in the appropriate CRF (eg, SLAB).

• For any laboratory tests with values considered clinically significantly abnormal during participation in the study or within 30 days after the last dose of study intervention, every attempt should be made to perform repeat assessments until the values return to normal or baseline or if a new baseline is established as determined by the investigator.

# 8.3.4.1 Laboratory Safety Evaluations (Hematology, Chemistry, and Urinalysis)

Laboratory tests for hematology, chemistry, and urinalysis are specified in Appendix 2.

Laboratory tests should be performed within 3 days before the first dose of study intervention. An exception is hepatitis and thyroid serologies, which may be performed within 28 days before the first dose. After Cycle 1, predose laboratory safety tests can be conducted up to 72 hours before dosing unless otherwise noted on the flow charts.

Laboratory test results must be reviewed by the investigator or qualified designee and found to be acceptable before administration of each dose of study intervention. Unresolved abnormal laboratory values that are drug-related AEs should be followed until resolution. Laboratory tests do not need to be repeated after the end of treatment if laboratory results are within normal range.

See the Operations/Laboratory Manual for additional details.

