# 1.3.1.2 Part 1, Arms 1 and 2, and Arm 1 Crossover to Arm 2: Posttreatment Phase

Table 2 Schedule of Activities: Posttreatment Phase for Part 1, Arm 1 and Arm 2, and Arm 1 Crossover to Arm 2

Study Phase:		Posttrea	tment		
Title:	Safe Follo		Imaging Follow-up	Survival Follow-up	Notes
Timing/frequency for Follow-up:	30 days after the last dose of study medication	Arm 2 only: 90 days after the last dose of pembrolizumab	Every 12 weeks	Every 12 weeks	
Scheduling Window (Days):	±7	±7	±7	±7	
Administrative Procedures					
Concomitant Medication Review	X	X			Arm 2: 90-day follow-up can be performed with a telephone call.
Anticancer Therapy Status	X			X	Any changes in new treatment will be collected.
Disease Status	X		X	X	See Sections 8.11.4.2 and 8.11.4.3.
Clinical Procedures / Assessments					
Full Physical Examination	X				
Vital Signs	X				Obtain heart rate, respiratory rate, blood pressure, temperature.
ECOG Performance Status	X				
AE Reporting	4		·		Arm 2: 90-day follow-up can be performed with a telephone call.
Vital Status	4			·	On Sponsor notification, all participants who do not/will not have a scheduled study visit or study contact during the Sponsor-defined time period will be contacted for their vital status.
Tumor Imaging Response Assessment			X		PCWG-modified RECIST 1.1 for prostate cancer participants; RECIST 1.1 for all other participants. Use the same type of scans obtained during treatment phase.
Laboratory Procedures / Assessments					
Comprehensive Chemistry Panel	X				
Hematology	X				
Thyroid Function Tests (TSH, T3 or free T3, free T4)	X				
Pharmacokinetics					
Plasma for MK-1088 PK	X				

AE=adverse event; ECOG=Eastern Cooperative Oncology Group; PCWG=Prostate Cancer Working Group; PK=pharmacokinetic; RECIST= Response Evaluation Criteria In Solid Tumors; TSH=thyroid-stimulating hormone.

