# 6.6.5 Immune-Related Events and Dose Modification (Withhold, Treat, Discontinue)

# Dose Modification and Toxicity Management for Immune-related AEs Associated with Pembrolizumab Monotherapy, Coformulations or IO Combinations

AEs associated with pembrolizumab monotherapy, coformulation, or IO combination exposure may represent an immune-related response. These irAEs may occur shortly after the first dose or several months after the last dose of pembrolizumab monotherapy, coformulation, or IO combination treatment and may affect more than one body system simultaneously. Therefore, early recognition and initiation of treatment is critical to reduce complications. Based on existing clinical study data, most irAEs were reversible and could be managed with interruptions of pembrolizumab monotherapy, coformulation, or IO combination administration of corticosteroids and/or other supportive care. For suspected irAEs, ensure adequate evaluation to confirm etiology or exclude other causes. Additional procedures or tests such as bronchoscopy, endoscopy, skin biopsy may be included as part of the evaluation.

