# 8.4.1 Time Period and Frequency for Collecting AE, SAE, and Other Reportable Safety Event Information

All AEs, SAEs, and other reportable safety events that occur after the participant provides documented informed consent, but before intervention allocation, must be reported by the investigator if the participant is receiving placebo run-in or other run-in treatment, if the event cause the participant to be excluded from the study, or is the result of a protocol-specified intervention, including, but not limited to washout or discontinuation of usual therapy, diet, or a procedure.

• All AEs from the time of intervention allocation through 30 days after cessation of study intervention must be reported by the investigator.

- All AEs meeting serious criteria, from the time of intervention allocation through 90 days after cessation of study intervention or 30 days after cessation of study intervention if the participant initiates new anticancer therapy, whichever is earlier, must be reported by the investigator.
- All pregnancies and exposure during breastfeeding, from the time of intervention
  allocation through the time required to eliminate systemic exposure after cessation of
  study intervention as described in Sections 5.1 and 8.3.5, or 30 days after cessation of
  study intervention if the participant initiates new anticancer therapy must be reported by
  the investigator.
- Additionally, any SAE brought to the attention of an investigator at any time outside the time specified above must be reported immediately to the Sponsor if the event is considered related to study intervention.

Investigators are not obligated to actively seek AEs or SAEs or other reportable safety events in former study participants. However, if the investigator learns of any SAE, including a death, at any time after a participant has been discharged from the study, and he/she considers the event to be reasonably related to the study intervention or study participation, the investigator must promptly notify the Sponsor.

All initial and follow-up AEs, SAEs, and other reportable safety events will be recorded and reported to the Sponsor or designee within the time frames as indicated in Table 11.

Exception: A positive pregnancy test at the time of initial screening is not a reportable event unless the participant has received study intervention.

PROTOCOL/AMENDMENT NO.: 002-01

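### Section 8.3.4.1 waives post-treatment laboratory tests after normal results, while Table 2 schedules them for everyone at the 30-day visit; the two need to be reconciled

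*Combined protocol and SAP*

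**What the plan says.** Section 8.3.4.1 (laboratory safety evaluations) ends its testing rules with two sentences. The first is "Unresolved abnormal laboratory values that are drug-related AEs should be followed until resolution". The second is "Laboratory tests do not need to be repeated after the end of treatment if laboratory results are within normal range". The second is not limited to the values described in the first. It also does not say which results must be normal, or whether the rule works panel by panel.

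Table 2 (Section 1.3.1.2, posttreatment phase) has a Safety Follow-up column timed "30 days after the last dose of study medication", with a window of 7 days either way. In that column the rows for the "Comprehensive Chemistry Panel", hematology and thyroid function are all marked, and the Notes column attaches no condition to them. Urinalysis is not in Table 2. Section 8.11.4.1 calls the 30-day visit mandatory.

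Section 8.3.4, the parent of 8.3.4.1, says that protocol-required laboratory assessments "must be conducted in accordance with the laboratory manual and the SoA".

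On the reporting window, Section 8.4.1 says: "All AEs from the time of intervention allocation through 30 days after cessation of study intervention must be reported by the investigator". Section 3 lists AEs among the primary endpoints, and Section 9.6.2 summarizes them by count and frequency for each dose level.

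**The concern.** The 30-day visit is the only post-treatment time point at which Table 2 schedules these panels, and it falls at the close of the window for nonserious AEs. An asymptomatic laboratory abnormality in that window is seen only if blood is drawn. The waiver is triggered by a normal result, so it would remove the scheduled draw from exactly those participants in whom any abnormality at day 30 would be new.

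The protocol expects late events. Of immune-related AEs under pembrolizumab, Section 6.6.5 says: "These irAEs may occur shortly after the first dose or several months after the last dose". Section 6.6.4 says much the same of AEs associated with MK-1088 and pembrolizumab. The hepatic event of clinical interest in Section 8.4.7 is defined wholly by transaminase, bilirubin and alkaline phosphatase values, so it cannot be identified without a sample. Section 4.1 says that late as well as early toxicities will inform confirmation of the final RP2D. At stake is whether laboratory AEs after treatment are ascertained in the same way in every participant and at every site.

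**Working it through.** The plan gives no figure to reproduce. The check sets the passages side by side and follows each reading through.

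1. **Where the waiver can act.** Table 1 already schedules chemistry, hematology and thyroid tests at the end-of-treatment/discontinuation visit. After that, Table 2 schedules them once, at 30 days. The additional Arm 2 contact at 90 days carries no laboratory panel and may be a telephone call. A waiver of scheduled tests after the end of treatment would therefore bear on the 30-day panels.

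2. **If Table 2 governs.** Everyone who attends is tested at discontinuation and again at day 30. Ascertainment does not depend on the earlier result.

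3. **If Section 8.3.4.1 is applied literally.** Participants with normal end-of-treatment results have no scheduled laboratory test from the discontinuation visit through day 30, while those with abnormal results are retested. Detection then depends on the previous result.

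4. **Which panels.** Chemistry and hematology are named in the heading of Section 8.3.4.1 and marked in Table 2, so the conflict is clear for them. Thyroid tests are less certain. The heading does not name them, Table 12 lists them under other tests, and Section 8.3.4.1 mentions thyroid serologies only for timing before the first dose. The waiver reaches them only through its unqualified reference to laboratory tests.

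5. **Which outputs.** Section 6.6.2 confines the DLT window to Cycle 1. DLT counts, the dose-finding decisions in Table 3 and the DLT-rate estimates are therefore largely unaffected. What could change is the summary of AEs and laboratory values after treatment.

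6. **Size.** The expected number of participants with a missed event would be N × s × p × a, where:
   - N is the number reaching the 30-day visit;
   - s is the share at sites that apply the waiver;
   - p is the share with normal end-of-treatment results;
   - a is the chance that such a participant develops a laboratory abnormality that would be judged an AE and is not found by a clinically prompted test.

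   The documents give only a planning figure of about 80 participants in Part 1, which bounds N. They give no s, p or a, and s could be zero, so the product cannot be computed.

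   The grain of the dose-level summaries can be stated. One participant is 1/14 = 7.1 percentage points at the planned maximum of 14 per dose level, and 1/3 = 33.3 points at the minimum of 3. That is the weight of one participant not already counted in the AE category. It does not estimate how many would be missed.

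**The case against.** The strongest reply is that the plan already says which text governs. Section 8.3.4 refers to the SoA for timing and frequency and uses mandatory language. Section 8 calls adherence to the SoA essential. Section 7.1 says that participants who stop treatment but stay in the study should complete the visits and procedures in the SoA. A site would have to prefer a permissive sentence to a mandatory one. This carries weight and makes literal use of the waiver less likely. It does not settle the matter, because Section 8.3.4.1 is the more specific text, sits under 8.3.4, and can be read as an exception to it. No text says which prevails.

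The second reply is that the sentence only ends the chain of repeat tests described just before it. Section 8.3.4 uses similar language about repeating abnormal tests until they return to normal. This reading is plausible and may be the intent. But the sentence is not confined to values under follow-up, and if that is all it means, saying so costs nothing. Section 8.3.4.1 also points to a laboratory manual that is not among the documents and may clarify the matter.

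The third reply is that other routes to detection remain, and this stands. Clinically prompted tests could find some events. A Discontinuation Visit falling at day 30 includes the follow-up procedures under Section 8.11.3. SAEs are collected to 90 days unless new anticancer therapy shortens that period. A day-30 sample would not, in any case, find events that begin months later.

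A reader might infer from the conflict that late laboratory AEs will in fact be found only in some participants. The documents do not support that. It follows only where sites act on Section 8.3.4.1 instead of the SoA.

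**Conclusion.** Wrong as written: Section 8.3.4.1 and Table 2 contradict each other on whether chemistry and hematology are drawn at the 30-day visit after normal results, and arguably on thyroid tests too. Where the waiver is applied literally, detection of asymptomatic laboratory AEs between discontinuation and day 30 would depend on the end-of-treatment result. Post-treatment AE and laboratory summaries could then be too low and uneven across sites.

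This conclusion assumes that at least some sites would follow Section 8.3.4.1, and that some abnormalities in the interval would be clinically significant and not prompt a test by themselves. An abnormal value becomes an AE only if the investigator judges it clinically significant (Section 10.3.2).

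Two further inferences should be resisted. One is a count of missed events: any such figure would rest on assumed rates with no source in the documents. The other is harm to dose escalation: DLTs are counted in Cycle 1, and Section 9.4.2 names DLT incidence as the primary safety endpoint. AEs remain one of the listed primary endpoints, so the contradiction is worth removing even though its effect is limited and of unknown size.

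**What to change.** Reconcile Section 8.3.4.1 with Table 2. One way is to state in Section 8.3.4.1 that the sentence does not waive the panels that Table 2 schedules at the 30-day Safety Follow-up Visit, and that it applies only to additional repeat tests beyond those in the SoA. The same edit should say whether thyroid tests are covered.

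If the sponsor does intend a waiver at day 30, the condition belongs in the Notes column of Table 2. The safety analysis section should then say that laboratory ascertainment after treatment depends on the end-of-treatment result.

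The first option costs one sentence and adds no visit, sample or procedure, because Table 2 already lists the draws.

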# 8.3.5 Pregnancy Testing

- Pregnancy testing:
  - Pregnancy testing requirements for study inclusion are described in Section 5.1.
  - Pregnancy testing ([urine or serum] as required by local regulations) should be conducted at monthly intervals during intervention.
  - Pregnancy testing ([urine or serum] as required by local regulations) should be conducted at the end of relevant systemic exposure and correspond with the time frame for female participant contraception in Section 5.1.

Additional serum or urine pregnancy tests may be performed, as determined necessary by the investigator or required by local regulation, to establish the absence of pregnancy at any time during the subject's participation in the study.

# 8.3.6 Eastern Cooperative Oncology Group Performance Status

The ECOG Performance Status is standardized criteria to measure how cancer impacts level of functioning (performance status) in terms of ability to care for oneself, daily activity, and physical ability (walking, working, etc.) with grades 0 to 5.

The investigator or qualified designee will assess ECOG status at screening, before the administration of each dose of study intervention at study visits, and during the follow-up period as specified in the SoA (Section 1.3).

# 8.4 Adverse Events, Serious Adverse Events, and Other Reportable Safety Events

The definitions of an AE or SAE, as well as the method of recording, evaluating, and assessing causality of AE and SAE and the procedures for completing and transmitting AE, SAE, and other reportable safety event reports can be found in Appendix 3.

Progression of the cancer under study is not considered an AE unless it results in hospitalization or death as described in Section 8.4.6 and Appendix 3.

Adverse events, SAEs, and other reportable safety events will be reported by the participant (or, when appropriate, by a caregiver, surrogate, or the participant's legally authorized representative).

The investigator and any designees are responsible for detecting, documenting, and reporting events that meet the definition of an AE or SAE as well as other reportable safety events. Investigators need to document if an SAE was associated with a medication error, misuse, or abuse. Investigators remain responsible for following up AEs, SAEs, and other reportable safety events for outcome according to Section 8.4.3.

The investigator, who is a qualified physician, will assess events that meet the definition of an AE or SAE as well as other reportable safety events with respect to seriousness, intensity/toxicity and causality.

Adverse events will not be collected for participants during the prescreening period (for determination of archival tissue status) as long as that participant has not undergone any protocol-specified procedure or intervention. If the participant requires a blood draw, fresh tumor biopsy, etc, the participant is first required to provide consent to the main study, and AEs will be captured according to guidelines for standard AE reporting.

# 8.4.1 Time Period and Frequency for Collecting AE, SAE, and Other Reportable Safety Event Information

All AEs, SAEs, and other reportable safety events that occur after the participant provides documented informed consent, but before intervention allocation, must be reported by the investigator if the participant is receiving placebo run-in or other run-in treatment, if the event cause the participant to be excluded from the study, or is the result of a protocol-specified intervention, including, but not limited to washout or discontinuation of usual therapy, diet, or a procedure.

• All AEs from the time of intervention allocation through 30 days after cessation of study intervention must be reported by the investigator.

- All AEs meeting serious criteria, from the time of intervention allocation through 90 days after cessation of study intervention or 30 days after cessation of study intervention if the participant initiates new anticancer therapy, whichever is earlier, must be reported by the investigator.
- All pregnancies and exposure during breastfeeding, from the time of intervention
  allocation through the time required to eliminate systemic exposure after cessation of
  study intervention as described in Sections 5.1 and 8.3.5, or 30 days after cessation of
  study intervention if the participant initiates new anticancer therapy must be reported by
  the investigator.
- Additionally, any SAE brought to the attention of an investigator at any time outside the time specified above must be reported immediately to the Sponsor if the event is considered related to study intervention.

Investigators are not obligated to actively seek AEs or SAEs or other reportable safety events in former study participants. However, if the investigator learns of any SAE, including a death, at any time after a participant has been discharged from the study, and he/she considers the event to be reasonably related to the study intervention or study participation, the investigator must promptly notify the Sponsor.

All initial and follow-up AEs, SAEs, and other reportable safety events will be recorded and reported to the Sponsor or designee within the time frames as indicated in Table 11.

Exception: A positive pregnancy test at the time of initial screening is not a reportable event unless the participant has received study intervention.

PROTOCOL/AMENDMENT NO.: 002-01

Table 11 Reporting Time Periods and Time Frames for Adverse Events and Other Reportable Safety Events

Type of Event	Reporting Time Period: Consent to Randomization/ Allocation	Reporting Time Period: Randomization/ Allocation through Protocol-specified Follow-up Period	Reporting Time Period: After the Protocol- specified Follow- up Period	Time Frame to Report Event and Follow-up Information to Sponsor:
NSAE	Report if: - due to protocol- specified intervention - causes exclusion - participant is receiving placebo run-in or other run-in treatment	Report all	Not required	Per data entry guidelines
SAE including Cancer and Overdose	Report if: - due to protocol- specified intervention - causes exclusion - participant is receiving placebo run-in or other run-in treatment	Report all	Report if: - drug/vaccine related. (Follow ongoing to outcome)	Within 24 hours of learning of event
Pregnancy/ Lactation Exposure	Report if: - participant has been exposed to any protocol-specified intervention (eg, procedure, washout or run-in treatment including placebo run-in) Exception: A positive pregnancy test at the time of initial screening is not a reportable event.	Report all	Previously reported  – Follow to completion/ termination; report outcome	Within 24 hours of learning of event
ECI (require regulatory reporting)	Report if: - due to intervention - causes exclusion	Report - potential DILI - require regulatory reporting	Not required	Within 24 hours of learning of event
ECI (do not require regulatory reporting)	Report if: - due to intervention - causes exclusion	Report - non-DILI ECIs and those not requiring regulatory reporting	Not required	Within 5 calendar days of learning of event

DILI=drug-induced liver injury; ECI=event of clinical interest; NSAE=nonserious adverse event; SAE=serious adverse event.

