#### 6 STUDY INTERVENTION

Study intervention is defined as any investigational intervention(s), marketed product(s), placebo, or medical device(s) intended to be administered to a study participant according to the study protocol.

Clinical supplies (study intervention[s]) provided by the Sponsor will be packaged to support enrollment and replacement participants as required. When a replacement participant is required, the Sponsor or designee needs to be contacted before dosing the replacement participant. Clinical supplies will be affixed with a clinical label in accordance with regulatory requirements.

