All concomitant medications received within 28 days before the first dose of study intervention and up to 30 days after the last dose of study intervention should be recorded. All concomitant medications administered during SAEs or ECIs are to be recorded. SAEs and ECIs are defined in Section 8.4.

Prohibited medications should not be used during the treatment phase of the study.

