#### 6.6.4 Guidelines for Dose Modification due to Adverse Events for MK-1088

Adverse events (both nonserious and serious) associated with MK-1088 and pembrolizumab exposure may represent an immunologic etiology. These AEs may occur shortly after the first dose or several months after the last dose of treatment.

For individual participants, dose delays and modifications of study treatment will be based on treatment-related toxicity, laboratory test results before treatment administration, and clinical assessments.

Participants may have up to 2 dose modifications of MK-1088 throughout the course of the study, as described in Table 7. Participants at dose level 1 who require dose reduction may reduce their dose to 50 mg. Participants who require dose reductions below 50 mg should be discontinued from study treatment. If further toxicity occurs or the criteria for resuming treatment are not met, the participant must be discontinued from the study intervention. If a participant experiences several toxicities and there are conflicting recommendations, follow the most conservative dose adjustment recommended (dose reduction appropriate to the most severe toxicity). Dose reductions are not permitted during the DLT evaluation period.

The NCI CTCAE, version 5.0 must be used to grade the severity of AEs. The investigator may attribute each toxicity event to MK-1088 alone, to pembrolizumab alone, or to the combination. However, dose modifications should be implemented according to Table 7, Table 8, and Table 9 regardless of investigator/Sponsor causality assessment and attribution to either or both drugs, unless clearly related to disease progression or intercurrent illness. If an irAE is observed in a participant enrolled on Arm 2, dose modifications for both pembrolizumab and MK-1088 should be followed according to the Grade associated with the AE in the respective dose-modification tables. If a participant experiences several toxicities and there are conflicting recommendations, follow the most conservative dose adjustment guidance.

Exceptional circumstances to following the dose-modification tables below may be considered after consultation with the Sponsor.

Table 7 MK-1088 Monotherapy: Dose Modification and Treatment Discontinuation Guidelines for Treatment Emergent Adverse Events

Toxicity	Hold Treatment	Criteria for Restarting Treatment	Dose/Schedule for Restarting Treatment	Criteria for Discontinuation after Consultation with Sponsor

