# 8.11.4.3 Survival Follow-up Contacts

Participant survival follow-up status will be assessed approximately every 12 weeks to assess for survival status until death, withdrawal of consent, or the end of the study, whichever occurs first.

The first survival follow-up assessment should be scheduled as described below:

- For participants who discontinue treatment intervention and who will not enter Efficacy Follow-up, the first survival follow-up contact will be scheduled 12 weeks after the Discontinuation Visit and/or Safety Follow-up Visit (whichever is last).
- For participants who completed assessments in Efficacy Follow-up, the first survival follow-up contact will be scheduled 12 weeks after the last efficacy assessment follow-up visit has been performed.

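### SAEs are reportable for 90 days after the last study intervention in both arms, but the only scheduled 90-day safety contact is in Arm 2 and is counted from the last pembrolizumab dose

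*Combined protocol and SAP*

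**What the plan says.** **Reporting window.** Section 8.4.1 sets two windows, neither of which depends on arm. For adverse events generally: "All AEs from the time of intervention allocation through 30 days after cessation of study intervention must be reported by the investigator". For serious events: "All AEs meeting serious criteria, from the time of intervention allocation through 90 days after cessation of study intervention", with the alternative "or 30 days after cessation of study intervention if the participant initiates new anticancer therapy, whichever is earlier, must be reported by the investigator".

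**What starts the clock.** Section 6 gives the term a broad meaning: "Study intervention is defined as any investigational intervention(s), marketed product(s), placebo, or medical device(s) intended to be administered to a study participant". Table 5 lists both MK-1088 and pembrolizumab, so in Arm 2 the window runs from whichever drug is stopped last.

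**Scheduled safety contacts.** Table 2 has a safety visit 30 days after the last study medication in both arms. The second safety column is headed "Arm 2 only: 90 days after the last dose of pembrolizumab". Each has a window of ±7 days, and the note on the AE Reporting row mentions the 90-day telephone option for Arm 2 alone. Sections 8.11.4, 8.11.4.1 and 8.11.5 describe the 30-day visit, or a call at 30 days if that visit was early, and nothing at 90 days.

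**Other contacts.** Section 4.1 has each participant telephoned every 12 weeks after discontinuation, for survival. Section 8.11.4.3 says that, for those not entering efficacy follow-up, "the first survival follow-up contact will be scheduled 12 weeks after the Discontinuation Visit and/or Safety Follow-up Visit", whichever is last. Participants who stop without progression continue scheduled imaging (Sections 8.2.4 and 8.11.4.2).

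**Expected timing of events.** On AEs of possible immunologic origin associated with MK-1088 and pembrolizumab, Section 6.6.4 says: "These AEs may occur shortly after the first dose or several months after the last dose of treatment".

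**The concern.** A reporting window is only as good as the contacts that feed it. The SAE rule covers both arms and runs from the last dose of any study drug. The contact that would serve it covers one arm and runs from one drug. Section 6.6.4 applies its warning about late events to MK-1088 as well as pembrolizumab, so the plan recognises the risk for the Arm 1 drug without scheduling a contact to ask about it.

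Safety and tolerability are the primary objective for both regimens. Section 8.4.2 commits to avoiding bias in detecting events and prefers open-ended verbal questioning. After Day 30 that questioning is scheduled as a safety contact in Arm 2 only, and in Arm 2 it may come before the window has closed. A non-fatal SAE in the uncovered days would then depend on being volunteered, or on surfacing at a contact made for another purpose.

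**Working it through.** The plan states no figure for this, so the check is a day count. Days are counted from the last dose of any study intervention unless stated otherwise.

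**Inputs**
- SAE window: 90 days, or 30 days if new anticancer therapy starts (Section 8.4.1).
- 30-day safety visit, ±7 days, both arms (Table 2).
- 90-day safety contact, ±7 days, Arm 2 only, from last pembrolizumab (Table 2).
- MK-1088 on Days 1 to 21, pembrolizumab on Day 1 of each cycle (Table 1).
- 12-weekly calls, 84 ± 7 days (Section 4.1); first survival contact 12 weeks after the later of two visits (Section 8.11.4.3).

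**Arm 1, no new anticancer therapy**
- Uncovered time = 90 − 30 = 60 days, or 60/90 = 67% of the window.
- Using Table 2's window alone: 90 − 37 = 53 days to 90 − 23 = 67 days. When the visit is early, Section 8.11.4 adds a call at Day 30, which brings the long end back to 60.
- Next contact, for survival: Day 84 (77 to 91) if counted from discontinuation as in Section 4.1. If counted from a Day 30 safety visit as in Section 8.11.4.3, it is 30 + 84 = Day 114 (107 to 121), after the SAE window has closed.

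**Arm 2, no new anticancer therapy**

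Let L be the days from the last pembrolizumab dose to the last MK-1088 dose. Counted from last pembrolizumab, the window closes at 90 + L and the contact falls at 90 ± 7. The shortfall is (90 + L) − (90 ± 7), which is L nominally and ranges from L − 7 to L + 7.

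| L (days) | Contact, days after last MK-1088 dose | Shortfall to Day 90 |
|---|---|---|
| 0 (both stop on the same day) | 90 (83 to 97) | 0 (−7 to 7) |
| 7 | 83 (76 to 90) | 7 (0 to 14) |
| 14 | 76 (69 to 83) | 14 (7 to 21) |
| 20 (MK-1088 through Day 21) | 70 (63 to 77) | 20 (13 to 27) |

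In the last row the window closes 20 + 90 = 110 days after the last pembrolizumab dose. The shortfall is 13/90 = 14% to 27/90 = 30% of the window.

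**Either arm, new anticancer therapy started**

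The window shortens to 30 days. The 30-day visit, which Section 8.1.5.2 requires before new therapy begun within 30 days, together with the Day 30 call in Section 8.11.4, covers it. There is no gap to close for these participants.

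**The case against.** The best defence is that the obligation to report does not differ by arm. Section 8.4 makes investigators responsible for detecting events. Section 8.4.1 makes a related SAE reportable at any time, and deaths would surface through survival and vital-status follow-up. On the Section 4.1 timing, every participant is also telephoned at about Day 84, and those without progression keep attending for scans. This stands as a limit on the consequence: the weak spot is non-fatal SAEs. It does not supply the missing contact, because neither the calls nor the scans are described as safety enquiries, and Section 8.11.4.3 can place the first survival call after Day 90.

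The AE Reporting arrow in Table 2 is not legible in the text available, so it might extend into the imaging follow-up column. The point therefore rests on the column headings, the row note and the text sections, and is limited to the legible schedule.

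Several stronger readings are tempting and are not supported:
- *That two thirds of the window is uncovered for every Arm 1 participant.* Those who start new anticancer therapy have a 30-day window, and the documents do not say how many that will be.
- *That the Arm 2 contact is always too soon.* The shortfall depends on L and is nominally zero when both drugs stop together. A longer gap, with MK-1088 continuing after pembrolizumab has stopped, would be an added assumption.
- *That Table 2 contradicts the text on nonserious events and medication.* Section 8.4.1 can be read as defining what is reportable at the contact. Section 6.5 asks for medications received "up to 30 days after the last dose of study intervention should be recorded", but its next sentence requires medications given during SAEs or ECIs as well. Only medication for late nonserious events is left unclear.
- *That the RP2D or a comparison of arms is biased.* Section 4.1 mentions late toxicities in connection with confirming the final RP2D across Parts 1 and 2. Allocation is nonrandom, AEs are summarised by dose level (Section 9.6.2), and no hypotheses are tested (Section 9.8).

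**Conclusion.** The mismatch is real in two respects: which arm has the contact, and which dose starts its clock. In Arm 1 about 60 days of the 90-day SAE window have no contact designated for safety. In Arm 2 the contact precedes the end of the window by 13 to 27 days when MK-1088 runs through Day 21 of the last cycle, and by nominally nothing when both drugs stop on the same day. Both statements apply only to participants who have not started new anticancer therapy, and the Arm 1 statement relies on the legible parts of Table 2.

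The consequence is a risk that late non-fatal SAEs are under-ascertained in the descriptive safety summaries. A reader might go further and infer that the arms will show a measured imbalance; the documents establish a difference in scheduled questioning, not in the events that will be recorded. The DLT endpoint is confined to Cycle 1 and is not touched. The correction is worth making prospectively, because events not asked about at the time may not be reliably recovered later.

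**What to change.** - **Table 2:** replace the Arm 2-only column with one telephone safety contact for both arms, at or shortly after 90 days from the last dose of any study intervention (for example Day 90 to +7), asking about SAEs since the 30-day visit. A one-sided window keeps the call from falling before the SAE window closes.
- **Exception:** keep the existing 30-day cut-off for participants who start new anticancer therapy.
- **Text:** align Sections 8.4.1 and 8.11.4.1 with this contact, so that the visit description, the reporting rule and the schedule name the same arms and the same starting dose.
- **Content of the contact:** state in Table 2 that it collects SAEs and their associated medications, consistent with Sections 8.4.1 and 6.5.

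The cost is one telephone call per Arm 1 participant, a later call date in Arm 2 (20 days later at nominal timing when MK-1088 runs through Day 21), and amendment wording. No dose, treatment rule or endpoint changes.
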